### **6.8 Visit 8**

Seizure frequency is assessed. Seizure Diary is reviewed. Medical history and physical examination are performed. Neurological examination is performed. CBC, CMP, and ASD trough levels are evaluated. An MRI of the brain with volume measurement is completed. An EEG is completed. PHQ-9, NDDI-E, MOCA, CGIC, C-SSRS and QOLIE-31 are completed. Neuropsychological follow-up assessment. Dispense study drug to participants in Group A (PER arm).

### **6.9 Visit 9**

Visit 9 will be complete by telephone call. Seizure Diary is reviewed Seizure frequency is assessed.. PHQ-9, NDDI-E,CGIC, C-SSRS and QOLIE-31 are completed by asking the participant the questions verbally. The participant will be asked about medical history.

### **6.10 Visit 10**

Visit 10 will be complete by telephone call. Seizure frequency is assessed. Seizure Diary is reviewed. PHQ-9, NDDI-E, CGIC, C-SSRS and QOLIE-31 are completed by asking the participant the questions verbally. The participant will be asked about medical history.

### **6.11 Visit 11**

Seizure frequency is assessed. Seizure Diary is reviewed. Medical history and physical examination are performed. Neurological examination is performed. An MRI of the brain with volume

Revised 23NOV2022

measurement is completed. An EEG is completed. PHQ-9, NDDI-E, MOCA, CGIC, C-SSRS and QOLIE-31 are completed. Neuropsychological follow-up assessment. Dispense study drug to participants in Group A (PER arm).

**6.12 Visit 12**

Visit 12 will be complete by telephone call. Seizure Diary is reviewed. Seizure frequency is assessed. PHQ-9, NDDI-E, CGIC, C-SSRS and QOLIE-31 are completed by asking the participant the questions verbally. The participant will be asked about medical history.

**6.13 Visit 13**

Visit 13 will be complete by telephone call. Seizure frequency is assessed. Seizure Diary is reviewed. PHQ-9, NDDI-E, CGIC, C-SSRS and QOLIE-31 are completed by asking the participant the questions verbally. The participant will be asked about medical history.

**6.14 Visit 14**

Visit 14 will be complete by telephone call. Seizure frequency is assessed. Seizure Diary is reviewed. PHQ-9, NDDI-E, CGIC, C-SSRS and QOLIE-31 are completed by asking the participant the questions verbally. The participant will be asked about medical history.

**6.15 Visit 15**

Medical history and examination are performed. Neurological examination is performed. Seizure Diary is reviewed. CBC, CMP, and ASD trough levels are evaluated. An EEG is ordered. MRI is reviewed. Seizure frequency is assessed. PHQ-9, NDDI-E, MOCA, CGIC, C-SSRS and QOLIE-31 are completed. Neuropsychological follow-up assessment.

**Schedule of Events**

Procedure	Screening & Baseline Visits 		Titration Phase 				Treatment Phase 								
			Day 7	Day 14	Day 21	Day 30	Day 60	Day 90	Day 120	Day 150	Day 180	Day 210	Day 240	Day 270	Day 300
Visit Day	Day 0-6														
Visit Number	1 	2 	3	4	5	6	7 	8	9 	10 	11	12 	13 	14 	15
Informed Consent	X														
Inclusion and Exclusion Criteria check 	X														
Medical/Surgical History	X		X	X	X	X	X	X	X	X	X	X	X	X	X
Concomitant medications	X		X	X	X	X	X	X	X	X	X	X	X	X	X
Neurological Examination	X					X		X			X				X
Physical Examination	X					X		X			X				X
Clinical Labs 	X							X			X				X
Historical Anatomical Brain MRI review 	X														
Anatomical Brain MRI 	X							X			X				X
Historical EEG review 	X														
Standard EEG 	X							X			X				X
Neuropsychology visit	X							X			X				X
NDDI-E	X		X	X	X	X	X	X	X	X	X	X	X	X	X

PHQ-9	X	X	X	X	X	X	X	X	X	X	X	X	X	X	X
MOCA	X	X	X	X	X		X			X					X
CGIC	X	X	X	X	X		X			X					X
C-SSRS	X	X	X	X	X	X	X	X	X	X	X	X	X	X	X
QOLIE-31	X	X	X	X	X	X	X	X	X	X	X	X	X	X	X
Urine Pregnancy Test	X														
Dispense Seizure Diary	X	X	X	X	X		X			X					
Seizure Diary Review		X	X	X	X	X	X	X	X	X	X	X	X	X	X
Adverse Event Assessment	X	X	X	X	X	X	X	X	X	X	X	X	X	X	X
Dispense Study Drug		X	X	X	X		X			X					
Study Drug Accountability		X	X	X	X		X			X					X

Clinical assessments (MRI, EEG, clinical labs, and anti-seizure drug levels) performed before or after scheduled follow-up if deemed clinically necessary outside of the study protocol.

±3-day tolerance window

CMP to include the following blood tests: albumin, blood urea nitrogen, calcium, carbon dioxide, chloride, creatinine, glucose, potassium, sodium, total bilirubin and protein, and liver enzymes (alanine aminotransferase, alkaline phosphatase, and aspartate aminotransferase).

 Screening and Baseline are preferred to occur consecutively on the same day but, if this is not feasible for the patient, the Baseline Visit procedures can occur any time after screening *and* before Day 7..All screening and baseline results must be available for review prior to dispensing study drug on day 7.

 Any development to the patient's history affecting their standing within the inclusion and exclusion criteria will be continually assessed throughout the study.

As needed and only for PER arm.

Baseline MRI and EEG performed only if one has not been performed within three months prior to baseline. , otherwise historical MRI and/or EEG will be reviewed .

Visits 7, 9, 10, 12, 13, and 14 will be completed as Phone Visits (PV).

±7-day tolerance window

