## 3 Study Design

### 3.1 General Description

This study is a prospective, open-label trial evaluating the effectiveness of PER on seizure frequency in adult patients with brain-tumor with seizures associated with high-grade glioma. Subjects (n = 20) will be male and female adults with a high-grade glioma recruited from Mayo Clinic in Jacksonville, Florida-[name], DO, (PI). Participants included will have had uncontrolled seizures, on a current regimen of at least 1 ASD manifesting ongoing focal seizures (including focal aware motor, focal impaired

awareness, and focal to bilateral tonic-clonic seizures), with at least 1 seizure/month during a retrospective 2-month baseline, relative to the screening visit.

All patients included in the study will follow STUPP protocol (radiotherapy plus concomitant and adjuvant Temozolomide) for treatment of high-grade glioma in addition to best medical practice of comorbidities, as is standard-of-care.

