### **3.5 Identification of Source Data**

Electronic medical records will be maintained via a RedCAP database for consecutive and prospective collection of data.

Efficacy measures used in the study include: clinical assessments will include serial brain MRI, EEG, anti-seizure drug levels and subject self-assessment at clinical follow-up; Neurological Disorders Depression Inventory for Epilepsy (NDDI-E), assessment for screening of depression PHQ-9;Montreal Outcome Cognitive Assessment (MOCA); Clinical Global Impression of Change (CGIC) score; Columbia –Suicide Severity Rating Scale. Seizure calendars performed at 2 months prior to initiation of therapy or adequate reliable historical baseline, and then monthly during study; and QOLIE-31, (see schedule of events for frequency of assessment).

Anatomic brain MRI with perfusion scanning/gadolinium will be obtained at 3 months and then every 3 months, to examine the correlated progression of brain tumor, or the absence of tumor. Laboratory studies will be employed before and after PER initiation. EEG will be obtained at baseline and at 3 months and 12 months to identify changes in background activity (e.g. diffuse slowing) and epileptiform discharges to correlate with focal seizure presence vs absence. Neuropsychological batteries will determine the presence or absence of significant anxiety, depression or cognitive changes over time and quality of life inventory will be obtained at the beginning, intermediate and end of the trial.

The following source data will be directly recorded on the Case Report Form (CRF):

- A comprehensive History and Physical examination and Neurological examination will occur at the initial screening/baseline.
- Clinical visitation will occur at screening/baseline, 3, 6, and 12 months.

Survey questionnaires will be obtained at baseline, 3, 6, 9, and 12 months. The following source data will not be directly collected in the Case Report Form (CRF), but will be captured in supportive documentation (study source documents, EMR):

- Laboratory studies will be employed at baseline and at each clinical visit after PER initiation.
- Brain tumor tissue will be assessed for the usual molecular markers (i.e., IDH-mutant vs wildtype, MGMT methylation, ARX).
- 12-lead ECG will be obtained at baseline and as clinically indicated
- Anatomic brain MRI with and without gadolinium will be obtained at baseline and follow-up brain MRI at 3 months and 6 months during PER use.

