### 4.2 Exclusion Criteria

1. Subject has serious cardiac, respiratory, renal, gastrointestinal, hematologic, or other medical condition as determined by the investigator to potentially interfere with the study
2. Subjects with glioblastoma not following Stupp protocol for treatment of glioblastoma.
3. History of status epilepticus in the 6 months prior to screening or a history of seizure clusters progressing to status epilepticus.
4. Past medical history of drug and/or alcohol abuse
5. Pregnant or breast-feeding
6. Subjects treated with PER prior to baseline
7. Prior felony conviction disclosed by the patient or previously stated in medical record.
8. History of violent behavior
9. Clinically significant laboratory abnormality at screening or baseline visits, as determined by the investigators
10. Use of an investigational drug or device within 20 days prior to treatment Day 1
11. Repeated radiation therapy for tumor regrowth
12. Subjects that plan to undergo tumor resection on or after baseline visit
13. Uncontrolled psychiatric disorder at baseline

14. Subjects who report active suicidal attempts or suicidality including subjects with a history of suicide attempts or suicidality determined to be clinically significant by investigators at screening.

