### **6.2 Visit 2 (Baseline)**

CBC, CMP, and ASD trough levels are evaluated. An MRI of the brain with volume measurement is completed. An EEG is taken if there has not been one completed within 3 months of the visit.

Revised 23NOV2022

Neuropsychological baseline visit. Seizure frequency is assessed. PHQ-9, NDDI-E, MOCA, CGIC, C-SSRS and QOLIE-31 are completed.

Screening and Baseline are preferred to be on the same day, but can occur separate days if needed. All screening and baseline events will be completed before Visit 3.

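### Footnote 7 lets an MRI up to three months old, possibly from before a resection, stand in for the baseline MRI that sections 6.2 and 3.5 call for, so measured tumour change can be wrong in size or sign.

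*Combined protocol and SAP*

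**What the plan says.** The plan describes the baseline MRI in two incompatible ways.

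- **Exemption.** Schedule of Events, footnote 7: "Baseline MRI and EEG performed only if one has not been performed within three months prior to baseline". Where a scan from that window exists, the footnote provides instead: "otherwise historical MRI and/or EEG will be reviewed". The schedule has a matching row, "Historical Anatomical Brain MRI review", so this is an intended route. No volume measurement is specified for the older scan.
- **No exemption for MRI.** Section 6.2: "An MRI of the brain with volume measurement is completed. An EEG is taken if there has not been one completed within 3 months". The three-month condition there attaches to the EEG only. Section 3.5 agrees that MRI is done at baseline: "Anatomic brain MRI with and without gadolinium will be obtained at baseline and follow-up brain MRI at 3 months and 6 months".

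On tumour treatment around that time, section 4.2 (criterion 12) excludes "Subjects that plan to undergo tumor resection on or after baseline visit", and criterion 11 excludes repeat radiotherapy for regrowth. Neither restricts a resection or a first course of radiotherapy before baseline. Section 3.1 says "All patients included in the study will follow STUPP protocol (radiotherapy plus concomitant and adjuvant Temozolomide) for treatment of high-grade glioma" but sets no timing relative to enrolment or to the scan.

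The baseline MRI is the reference for the secondary objective on MRI progression against alternate ASDs (section 2) and for Secondary Hypothesis 1 (section 7.2), which compares it with an MRI at 12 months. The last MRI in the schedule is at Day 300. Study drug is first dispensed on Day 7.

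**The concern.** A change from baseline describes the study period only if the baseline shows the tumour as it was when the study period began. Under footnote 7 it may not. If a resection falls between the older scan and the baseline visit, the volume removed by surgery is counted as change on study. If nothing intervenes, up to three months of earlier growth is counted instead.

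The first error makes a treatment look active against the tumour; the second makes it look worse. Section 1.1 asks whether perampanel has a cytotoxic effect on tumour, so a false shrinkage signal in that arm would bear directly on the study's rationale. The errors need not cancel between arms. Section 4.3 lets the treating physician choose the arm, so scan age and recent surgery may differ between the two groups of 10. The only methods named in section 7.2 are the t-test and chi-square, which adjust for neither.

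**Working it through.** The plan gives no figure to reproduce here: section 7.1 sets 20 patients without an effect size, SD or power. The check is of what footnote 7 does to a measured change.

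**Inputs from the plan.** Look-back of three months, about 91 days; MRI at Days 90, 180 and 300; 10 patients per arm. The baseline visit is taken as Day 0.

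**Assumptions (the plan gives none).** Fraction of volume removed before baseline, r; true change on study, g; volume doubling time, T.

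**1. Interval.** Interval = follow-up day + scan age.
- Day 90: 90 + 91 = 181 days; 181/90 = 2.01.
- Day 180: 180 + 91 = 271 days; 271/180 = 1.51.
- Day 300: 300 + 91 = 391 days; 391/300 = 1.30.

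The last line is the relevant one for Secondary Hypothesis 1, since Day 300 is the last scheduled MRI. With a scan on Day 0 all three ratios are 1.

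**2. Size, no treatment in between.** Change = 2^(t/T) − 1.

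| T (assumed) | Follow-up | From Day 0 | From a 91-day-old scan |
|---|---|---|---|
| 180 days | Day 90 | 41% | 101% |
| 180 days | Day 300 | 217% | 351% |
| 365 days | Day 90 | 19% | 41% |
| 365 days | Day 300 | 77% | 110% |

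**3. Sign, resection in between.** Measured change = (1 − r)(1 + g) − 1, which is negative when r > g/(1 + g).
- g = 25%: 0.25/1.25, so the sign flips above 20% removed.
- g = 50%: 0.50/1.50, above 33%.
- g = 100%: 1.00/2.00, above 50%.
- Example: r = 50%, g = 25% gives 0.5 × 1.25 − 1 = −37.5%.

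The reverse also occurs. A true 20% shrinkage reads as growth if the tumour grew more than 25% between the older scan and baseline, since 1.25 × 0.80 = 1.00.

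**4. Arm mean.** Suppose the true change is +25% in every patient and three of 10 in one arm have a pre-resection scan with r = 50%. That arm's mean is (3 × (−37.5) + 7 × 25)/10 = +6.25%, a spurious difference of 25 − 6.25 = 18.75 points. The three is illustrative.

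**5. Does a simple rate repair it?** With T = 180 days, 41%/90 = 0.46% per day but 101%/181 = 0.56% per day, so percent change per day still depends on scan age. Change in log volume per day is ln 2/180 = 0.00385 in both cases. Under constant exponential growth the log scale removes the dependence. No rate removes the step caused by a resection.

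**The case against.** The strongest reply is that sections 6.2 and 3.5 both call for a baseline MRI; if they govern, there is no problem. Footnote 7 also says only that the older scan is reviewed, so its use as the reference volume is an inference. That is fair, but no passage says which text governs. Under footnote 7 a patient with a recent scan has no other baseline image, so the older scan is the only one available for the comparison.

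A second reply is that medical and surgical history is scheduled through the study and MRI is kept in source records, so scan dates and intervening surgery should be recoverable. That stands, and it supports a sensitivity analysis. It does not supply a post-resection volume that was never imaged.

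Three stronger readings are tempting but unsupported:

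- *Recent tumour treatment is the norm, so sign reversal is typical.* Section 3.1 sets no timing, the regimen includes an adjuvant phase, and grade II tumours are eligible. Patients may be well past surgery and radiotherapy. Reversal is possible; its frequency is unknown.
- *The planned analysis carries a two-fold error.* That ratio belongs to Day 90. At Day 300 it is 1.3. Section 7.2 refers to image fusion and defines no percent-volume endpoint, so the percentages above are illustrations.
- *A fresh scan removes radiation effects.* Nothing requires radiotherapy to be complete by baseline, so a Day 0 scan before or during a course would still mix radiation change into follow-up.

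A reader might also want a short fixed window such as four weeks. The documents give no basis for one. If scan ages were spread evenly over 0 to 91 days (an assumption), (91 − 28)/91 = 69% of patients with a qualifying scan would need a new one.

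**Conclusion.** The concern holds in a limited form. Footnote 7 contradicts sections 6.2 and 3.5 and, if followed, permits a reference scan up to about 91 days old that may precede a resection. The interval error is at most 1.3-fold at Day 300 and about 2-fold at Day 90. The sign of the change reverses whenever the fraction removed exceeds g/(1 + g).

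The interval figures rest on the plan's own visit days and look-back. The percentages rest on assumed growth, resection fractions and doubling times. The documents support no statement about how many patients would be affected or which arm would be favoured.

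The reach is narrow: the secondary MRI analyses of a pilot that section 7.1 says is not powered for effectiveness. None of the endpoints listed in section 3.4 uses the baseline MRI. It is worth correcting because the change is small and a baseline volume not obtained cannot be recovered later.

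**What to change.** 1. Reconcile footnote 7 with sections 6.2 and 3.5 so that one rule applies.
2. Accept an older MRI as baseline only if it postdates the most recent resection, no radiotherapy course was started or completed between the scan and the baseline visit, and tumour volume is measured on it. Otherwise perform the baseline MRI already listed in section 6.2.
3. Record the scan date and any tumour treatment between scan and baseline on the CRF.
4. Analyse change in log volume per unit time from the actual scan date, with a sensitivity analysis excluding patients whose scan predates an intervening treatment.

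The cost is amendment wording, two recorded items, and a baseline MRI for some patients who would otherwise have relied on an older scan. How many cannot be derived from the documents, but section 6.2 already lists that MRI for everyone. Radiation change arising after a valid baseline scan is a separate confounder that this fix does not remove.

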## 7 Statistical Plan

### 7.1 Sample Size Determination

A sample size of 20 patients is targeted as part of a pilot study to determine feasibility for a larger prospective multi-center trial. The sample size is targeted to achieve adequate enrollment and determine the likelihood of supporting a larger study.

This study is not designed to be powered to determine significance for statistical significance of effectiveness.

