## 2 Study Objectives

### Primary Objective

Demonstrate the efficacy and safety of PER on seizure frequency in adult patients with biopsy-proven high-grade glioma and focal Epilepsy compared with alternate ASDs.

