#### **4.3 Subject Recruitment, Enrollment and Screening**

Subjects (n = 20), will be male and female adults with a high-grade glioma recruited from Mayo Clinic in Jacksonville, Florida- [name], DO, (PI). 10 subjects will be enrolled into an adjunctive Perampanel and other ASDs group, and 10 subjects will receive only alternative ASDs. There will be a 6-month recruitment period for screening and enrollment. The treating physician will decide, based on best medical practice, which patients are candidates for adjunctive Perampanel and other ASDs, or only alternative ASDs. Patients taking Perampanel will begin their titration phase upon enrollment.

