#### Handling of Missing Data

Study data will be collected and managed using REDCap electronic data capture tools hosted at Mayo Clinic. All data requested on the Case Report Form (CRF) will be recorded for each participant. A standardized CRF will be generated by REDCap. For any data query, the Principal Investigator and Investigators will meet to clarify the data queried and make corrections based on consensus. Once the study is completed, the Principal Investigator will randomly select 3 participants and compare the data documented for each on the CRF with what is entered into the REDCap database. If there is any discrepancy, the Principal Investigator and/or Investigators will cross-reference all 20 patients to ensure accuracy.

**Primary Hypothesis:** We hypothesize that perampanel will lead to a significant reduction in seizure frequency for adult patients with brain tumor-related seizures associated with high-grade glioma.

We will compare seizure frequency before and 3 months after treatment with monotherapy and adjunctive PER and use descriptive statistics to demonstrate differences in responders. A P-value < 0.05 will be used to reflect statistical significance.

**Secondary Hypothesis 1:** We hypothesize the progression of brain tumor (comparing 4 and 8 mg/d of perampanel) based upon fusion by comparing baseline brain MRI and MRI at 12 months will be less for IDH-mutants.

We hypothesize there will be minimal or no change in neurocognitive function from 0 to 3 months on Montreal Outcome Cognitive Assessment (MOCA; higher scores indicating greater function); and the Clinical Global Impression of Change (CGIC; scores from 1 to 7, with lower scores indicating greater improvement and a score of 4 indicating no change).

Chi-square and Student T-test will be used to measure differences in assessment and change during the study period. A P-value < 0.05 will be considered significant.

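### The sample of 20 is justified by feasibility and power is disclaimed, yet hypotheses are judged at P<0.05 and no feasibility outcome or progression criterion is prespecified

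*Combined protocol and SAP*

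**What the plan says.** Section 7.1 gives one reason for the sample size: "A sample size of 20 patients is targeted as part of a pilot study to determine feasibility for a larger prospective multi-center trial". It adds: "The sample size is targeted to achieve adequate enrollment and determine the likelihood of supporting a larger study". It then disclaims power: "This study is not designed to be powered to determine significance for statistical significance of effectiveness". Section 4.3 splits the 20 evenly: "10 subjects will be enrolled into an adjunctive Perampanel and other ASDs group, and 10 subjects will receive only alternative ASDs". The treating physician chooses the group.

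The rest of the plan is clinical. The primary objective in section 2 is: "Demonstrate the efficacy and safety of PER on seizure frequency in adult patients with biopsy-proven high-grade glioma and focal Epilepsy compared with alternate ASDs". The endpoints in section 3.4 are seizure responders, overall survival and neuropsychological decline. In section 7.2 (under Handling of Missing Data) the primary hypothesis reads: "We hypothesize that perampanel will lead to a significant reduction in seizure frequency". That section sets P<0.05 for the primary hypothesis and again for the secondary ones. The named tests are Student's t-test and chi-square. Section 7.2 also plans descriptive statistics for responders, and an interim analysis of safety and efficacy at half enrollment.

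No objective, endpoint, hypothesis or analysis in sections 2, 3.4 or 7 concerns recruitment, retention, adherence or data completeness.

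**The concern.** A feasibility pilot need not be powered for efficacy, and this plan says openly that it is not. The difficulty lies in what follows. The one decision standard the plan states is a significance threshold on clinical outcomes, which is the kind of conclusion section 7.1 says the study is not sized to reach. The question section 7.1 does pose, whether a larger multi-center trial can be supported, has no defined measure, no planned estimate and no target.

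Two things are at stake. A real and sizeable difference in response would most likely be reported as not significant. And when the study ends, whoever decides on the larger trial will have no prespecified result to decide from, so the feasibility criteria would have to be chosen after the data are known.

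**Working it through.** **Inputs from the documents.** N = 20 (sections 3.2 and 7.1); 10 per group (section 4.3); significance level 0.05, with t-test and chi-square (section 7.2); 6-month recruitment period (section 4.3).

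**Assumptions.** Two-sided testing, because sidedness is not stated. All responder rates and standardised effects below are illustrative; the documents give none.

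**1. The plan's own figure.** N = 20 cannot be reproduced. No effect size, responder rate, standard deviation, power, dropout or precision target is stated. This agrees with the disclaimer in section 7.1 and is not an error in itself.

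**2. Power of a between-arm responder test.** This is one reading of sections 2 and 7.2. Exact power sums, over all outcomes a and b from 0 to 10,

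Bin(a; 10, p1) × Bin(b; 10, p2) × [1 if the test gives P<0.05, else 0].

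| Assumed rates | Chi-square, uncorrected | Fisher |
|---|---|---|
| 40% vs 20% | 13% | 6% |
| 50% vs 20% | 25% | 13% |
| 60% vs 20% | 42% | 25% |
| 80% vs 20% | 81% | 64% |

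The plan names chi-square. Fisher is shown because cell counts this small often lead to it in practice.

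**3. What one plausible result would look like.** Suppose 5/10 versus 2/10 respond.
- Uncorrected chi-square = 20 × (5×8 − 5×2)² / (7 × 13 × 10 × 10) = 18000/9100 = 1.98, below the 3.84 needed for P<0.05. Fisher P = 0.35.
- Wilson 95% limits are 0.237 to 0.763 for 5/10 and 0.057 to 0.510 for 2/10.
- Newcombe lower limit: 0.30 − √[(0.500−0.237)² + (0.510−0.200)²] = 0.30 − 0.407 = −0.107.
- Newcombe upper limit: 0.30 + √[(0.763−0.500)² + (0.200−0.057)²] = 0.30 + 0.300 = 0.600.

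The interval of about −11 to +60 percentage points includes no difference and a very large benefit.

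**4. The before/after comparison.** Section 7.2 also describes seizure frequency before treatment against 3 months after. For a paired t-test in one group of 10, power is the probability that a noncentral t with 9 degrees of freedom and noncentrality d√10 exceeds 2.262 in absolute value. This gives 29% at d = 0.5, 62% at d = 0.8 and 80% at d = 1.0.

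**5. What 20 subjects can say about feasibility.**
- Enrolling 20 in 6 months is 20/6 = 3.3 per month; the exact Poisson 95% interval is 2.0 to 5.1.
- If 16/20 were retained (80%), the exact 95% interval would be 56% to 94%.
- If 8/10 PER subjects met the tolerance condition (80%), it would be 44% to 97.5%.

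These are coarse but usable estimates.

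**6. What is collected against what is defined.**

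| Raw data | Where | Defined as an outcome or given a criterion? |
|---|---|---|
| Consent counts, every two weeks | Section 10.1, DSMP item 7 | No |
| 6-month recruitment period | Section 4.3 | A time frame only |
| Titration and tolerance condition for staying in the study | Section 5.3 | No |
| Drug accountability | Schedule of Events | No |
| Diary review, Visits 3 to 8 up to Day 90 | Sections 6.3 to 6.8 | No |
| Visit attendance to Day 300 | Schedule of Events | No |

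**The case against.** The strongest reply is that nothing is hidden. Section 7.1 discloses the lack of power, and stating a 0.05 threshold alongside that disclosure is not a logical contradiction. The synopsis says 'evaluate'; only section 2 says 'Demonstrate'. The paired comparison has more power than the between-arm test: 62% at d = 0.8, and 80% at d = 1.0. These points stand, and they keep this from being a criticism of the sample size.

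A reader might also infer three stronger things that the documents do not support.
- *That the trial is analysed only by significance tests on efficacy.* Section 7.2 also plans descriptive statistics for responders, and safety is part of both the primary objective and the interim analysis. Still, no estimate or interval is specified, and the sentence after the one on responders applies P<0.05.
- *That feasibility is not measured, so the study cannot answer its own question.* The data in step 6 will exist, and accrual and retention could be described from them. What is absent is a named outcome and a target.
- *That the go/no-go for the larger trial would rest on a P-value.* No text makes that link. Section 7.1 ties the larger trial to enrollment and the likelihood of supporting it, without saying how either will be judged.

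**Conclusion.** The point holds in this form: the stated purpose and the stated analysis do not match, and the purpose has no prespecified measure or decision rule. Disclosing low power does not close that gap, because the plan still sets significance as its standard and puts nothing in place for feasibility.

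On size, a between-arm responder comparison has roughly 25% to 42% power by uncorrected chi-square (13% to 25% by Fisher) if response is 50% to 60% against 20%. About 80% power needs a gap as wide as 80% against 20%, and then only by chi-square. The before/after test in 10 subjects needs a standardised effect of about 1.0. These figures rest on assumed rates and effects, two-sided 0.05 and no losses. Deaths or withdrawals that reduce the number analysed would lower them further.

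The plan should be changed on this point. An unpowered sample of 20 is acceptable for a pilot and need not change.

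**What to change.** Edit sections 2, 3.4 and 7.2 and the matching synopsis rows (objectives and Statistical Methodology).

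1. Replace the P<0.05 rule for all clinical outcomes, secondary ones included, with estimates and 95% CIs labelled exploratory. Apply the same to the efficacy part of the interim analysis. State that the physician chooses the group, so the intervals reflect sampling error and not selection.
2. In section 2, change 'Demonstrate' to 'Estimate'.
3. Add feasibility outcomes from data already collected:
   - subjects enrolled within the 6-month recruitment period, against 20;
   - share of PER subjects who meet the plan's own titration and tolerance condition (section 5.3 and DSMP item 1 describe the titration interval differently, and must be reconciled before this outcome is defined);
   - share of subjects with seizure-diary data reviewed at every scheduled visit to Day 90;
   - retention to Day 300, with deaths reported separately from dropout.
4. Have the sponsor set a progression target for each outcome before the data are reviewed. Only accrual has a figure now.
5. State that the decision on a larger trial rests on these outcomes.

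This needs no new visits, subjects or data. The cost is the loss of any significance claim, which section 7.1 already disclaims.
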